## 28 TRIAL FUNDING

The CEDAR trial is funded in part by the Clinical Research Committee (Early Phase & Feasibility Studies) on behalf of Cancer Research UK (CRUK/17/015). The Oncology Clinical Trials Office is supported by Cancer Research UK core funding. PsiOxus Therapeutics Limited are providing a grant and enadenotucirev to support the trial. This trial is further supported via the University of Oxford core clinical and research infrastructure underpinned by strategic research programme grant funds. This trial is on the NIHR portfolio; local research network support should be available at each site taking part to support entry of participants into this trial.

## 29 SPONSORSHIP AND INDEMNITY

### 29.1 Sponsorship

The Sponsor will provide written confirmation of Sponsorship and authorise the trial commencement once satisfied that all arrangements and approvals for the proper conduct of the trial are in place. A separate trial delegation agreement, setting out the responsibilities of the Chief Investigator and Sponsor will be put in place between the parties.

### 29.2 Indemnity

The University has a specialist insurance policy in place which would operate in the event of any participant suffering harm as a result of their involvement in the research (Newline Underwriting Management Ltd, at Lloyd's of London). NHS indemnity operates in respect of the clinical treatment which is provided.

### 29.3 Contracts/Agreements

This trial is subject to the Sponsor's policy requiring that written contracts/agreements are agreed formally by the participating bodies as appropriate. A Clinical Trial Agreement (CTA) will be placed between the Sponsor and participating organisations prior to site activation.

The Sponsor will also set up written agreements with any other external third parties involved in the conduct of the trial as appropriate.

## 30 PUBLICATION POLICY

The sponsor will retain ownership of all data arising from the trial. The intention is to publish this research in a specialist peer reviewed scientific journal on completion of the trial. The results may also be presented at scientific meetings and/or used for a thesis. The Investigators will be involved in reviewing drafts of the manuscripts, abstracts, press releases and any other publications arising from the trial and retain final editorial control. Authors will acknowledge that the trial was Sponsored by and performed with the support of the Sponsor and other funding bodies as appropriate.

**APPENDIX 1: ECOG PERFORMANCE SCALE**

Activity Performance Description	Score
Fully active, able to carry out all on all pre-disease performance without restriction.	0
Restricted in physically strenuous activity but ambulatory and able to carry out work of a light or sedentary nature, e.g. light housework, office work.	1
Ambulatory and capable of all self-care, but unable to carry out any work activities. Up and about more than 50% of waking hours.	2
Capable of only limited self-care. Confined to bed or chair more than 50% of waking hours.	3
Completely disabled. Cannot carry out any self-care. Totally confined to bed or chair.	4

**APPENDIX 2: MRI ASSESSED TUMOUR REGRESSION GRADING (mrTRG)**

TRG score	mrTRG description
1	No/minimal fibrosis visible (tiny linear scar) and no tumour signal
2	Dense fibrotic scar (low signal intensity) but no macroscopic tumour signal ( indicates no or microscopic tumour )
3	Fibrosis predominates but obvious measureable areas of tumour signal visible
4	Tumour signal predominates with little/minimal fibrosis
5	Tumour signal only: no fibrosis, includes progression of tumour

For the purposes of trial analysis and dose escalation, scores of 1 or 2 will be classified as responders and scores of 3, 4 or 5 will be classified as non-responders.

**APPENDIX 3: NEOADJUVANT RECTAL SCORE**

$$NAR = \frac{[5 \ pN - 3(cT - pT) + 12]^2}{9.61}$$

Where:

cT is an element of the set {1, 2, 3, 4},

pT is in {0, 1, 2, 3, 4},

pN is in {0, 1, 2}.

cT clinical tumour stage,

pT pathologic tumour stage,

pN pathologic nodal stage

The neoadjuvant rectal score (47) outperforms pCR at predicting DFS and OS in clinical trials using neoadjuvant therapy for rectal cancer. It similarly performs well at predicting DFS and OS in trials using pre-op chemo and chemoradiotherapy (TNT). It is an NCI-approved short-term endpoint for phase II clinical trial performance. The final score ranges from 0-100 where a higher score equates to a worse prognosis.

## 1. INTRODUCTION

This document details the proposed data presentation and analysis for the main paper(s) and final study reports from the Cancer Research UK & PsiOxus Therapeutics Limited Multicentre of intravenous EnAdenotucirev in combination with chemoradiotherapy in the treatment of locally advanced rectal cancer (CEDAR). The results reported in these papers should follow the strategy set out here. Subsequent analyses of a more exploratory nature will not be bound by this strategy, though they are expected to follow the broad principles laid down here. The principles are not intended to curtail exploratory analysis (for example, to decide cut-points for categorisation of continuous variables), nor to prohibit accepted practices (for example, data transformation prior to analysis), but they are intended to establish the rules that will be followed, as closely as possible, when analysing and reporting the trial.

The analysis strategy will be available on request when the principal papers are submitted for publication in a journal. Suggestions for subsequent analyses by journal editors or referees, will be considered carefully, and carried out as far as possible in line with the principles of this analysis strategy; if reported, the source of the suggestion will be acknowledged.

Any deviations from the statistical analysis plan will be described and justified in the final report of the trial. The analysis should be carried out by an identified, appropriately qualified and experienced statistician, who should ensure the integrity of the data during their processing. Examples of such procedures include quality control and evaluation procedures.

### 1.2 Changes from previous version of SAP

A summary of key changes from earlier versions of SAP, with particular relevance to protocol changes that have an impact on the design, definition, sample size, data quality/collection and analysis of the outcomes will be provided. Include protocol version number and date.

Version number Issue date	Author of this issue	Protocol Version & Issue date	Significant changes from previous version together with reasons
V1.0_20Jan2020	[name], [name]	Protocol_V2.0_20Nov2019	Not applicable as this is the 1 st issue
V2.0_04Jan2021	[name], [name]	Protocol_V3.0_11Aug2020	Updated to be in line with most recent protocol

## 2. BACKGROUND AND OBJECTIVES

### 2.1 Background and rationale

Full Title :	A Phase 1 trial of the safety, tolerability and biological effects of intravenous enadenotucirev, a novel oncolytic virus, in combination with chemoradiotherapy in locally advanced rectal cancer	
Short Title:	Chemoradiation with Enadenotucirev as a radiosensitiser in locally Advanced Rectal cancer	
Trial Acronym:	CEDAR	
Clinical Phase:	Phase 1	
Trial Design:	Interventional	
	Objectives	Endpoints
Primary Endpoint:	Determine the optimal dose and frequency of enadenotucirev that can be administered with chemoradiation	

• Dose limiting toxicities

• MRI tumour regression grade

Secondary Endpoints:	Ability to deliver enadenotucirev concurrently with chemoradiation	Treatment tolerance measured by proportion of patients completing at least 80% of the prescribed capecitabine dose and at least 20 fractions of radiotherapy
	To measure local response rate to combined therapy	

• MRI tumour regression grade

• Pathological complete response rate

• Neoadjuvant rectal score

Investigational Medicinal Product(s)	Name of drug	Formulation, dose, route of administration
	

- Enadenotucirev

- Capecitabine

	
Solution, diluted and delivered intravenously
 
There are 2 potential doses given over 4 different dosing levels:
 

• <math>1 \times 10^{12}</math> vp (viral particles)

• <math>3 \times 10^{12}</math> vp

 
- Tablet, 900mg/m^2, oral administration

Other interventions:	Neoadjuvant chemoradiotherapy	
Treatment Duration	9 weeks	
Follow-up duration	Trial follow-up visits continue until week 13. Following this, patients will receive surgery and on-going follow up as standard of care.	
End of Trial	Last Patient Last Visit (i.e. 4-6 weeks post-surgery visit)	

### 2.2 Objectives

Primary Objective	Endpoints/ Outcome measures	Time point(s) of evaluation of this end point

 
Determine the optimal dose and frequency of enadenotucirev that can be administered with chemoradiation
 
	
 
Dose limiting toxicity
 
MRI tumour regression grade
 
	
 
From Day 1 to Week 13
 
Week 13
 

Secondary Objectives	Endpoints	

 
Ability to deliver enadenotucirev concurrently with chemoradiation
 
To measure local response rate to combined therapy compared to pre-treatment status
 
	
 
Treatment tolerance measured by proportion of patients completing at least 80% of the intended Capecitabine dose and at least 20 fractions of radiotherapy
 
MRI tumour regression grade
 
Pathological complete response
 
Neoadjuvant Rectal (NAR) score
 
	
 
Week 9
 
Week 13
 
Post resection
 
Post resection
 

Tertiary/Exploratory Objectives	Endpoints	

 
To identify 'proof of concept' that enadenotucirev replicates in the tumour
 
	
 
IHC staining of hexon protein coat, viral gDNA and viral mRNA gene expression in tumour cells
 
	
 
Archival tumour tissue
 
Week 4 biopsy
 
Resection sample
 

 
To analyse gene expression changes in rectal cancer in response to enadenotucirev
 
	
 
Whole genome RNA expression via RNA sequencing/ Nanostring gene expression analysis
 
	
 
Archival tumour tissue
 
Week 4 biopsy
 
Resection sample
 

 
Analyse changes in circulating tumour DNA in response to chemoradiation and enadenotucirev
 
	
 
ctDNA analysis exploring clearance of ctDNA and any/or emerging changes in persisting ctDNA
 
	
 
Baseline (Pre 1st loading dose)
 
Week 4
 
Week 13
 
4-6 weeks post-surgery
 


 
Assess the changes in microbiome taxa during therapy
 
	
 
Extraction of DNA and 16S sequencing and meta-transcriptomics from faecal samples
 
	
 
Baseline (pre-enad)
 
End of week 1 / 2
 
End of week 4
 
End of week 7
 
Week 13
 

 
Analyse the immune microenvironment as evidenced by immune cell infiltrates
 
	
 
Multiplex immunohistochemistry of immune cell markers
 
	
 
Archival tumour tissue
 
Week 4 biopsy
 
Resection sample
 

Note: Objectives in grey are not described in this SAP and will not be undertaken by the trial statistician.

### 3. STUDY METHODS

#### 3.1 Trial Design/framework

Provide a brief description of trial design including type of trial (e.g. parallel group, multi-arm, cross-over, factorial), and brief description of the interventions.

Describe the framework such as superiority, non-inferiority, equivalence including which comparisons will be presented on this basis.

This is a dual-endpoint dose finding phase I trial. The trial will use a model-based approach using the toxicity and efficacy primary endpoints to recommend the treatment schedule for future patients, and to recommend the optimal dose at the trial's conclusion.

We are using both efficacy and toxicity endpoints because although toxicity is expected to increase with increasing dose, it is possible that the relationship between efficacy and dose may not be a monotonically increasing one. This means that the optimal dose may not be the maximum tolerated dose. However there will be no formal combination of the efficacy and toxicity data, both endpoints will contribute information independently to dose choice via dose escalation rules.

### **3.2 Randomisation and Blinding**

This is not a randomised trial.

### **3.3 Sample Size**

At most, 30 patients will be recruited. Simulations have been used to justify this sample size, results are given in Appendix 1.

### **3.4 Statistical Interim Analysis, Data Review and Stopping guidelines**

The TMG will meet as necessary to discuss toxicity data and to decide on dose escalation. The first interim analysis will occur after the first 2 patients have been followed for 13 weeks. Subsequently there will be an interim analysis each time a dose-escalation decision is required. The TMG will include Chief Investigator, Co-Investigators, clinical Trial Manager, Trial Statistician and others as required. TMG membership and decision making procedures are documented in the TMG charter (V1.0, 26th November 2019) and is stored in the TMF.

Dose-escalation decisions will be based on all currently available data and guided by the pre-specified model. Analysis will follow the methods for primary analysis and are described in Section 6.2.1

The template for the first TMG dose decision report is given in Appendix 2. Changes may be made to this template as the trial progresses, but note that the original template will not be updated as it refers only to the first dose decision meeting.

There is no independent Data and Safety Monitoring Committee (DSMC) for this trial. The Safety Review Committee (SRC) will be convened as required to review DLTs and dose escalation decisions, made by the TMG. In the event of the TMG being unable to conclude on a dose recommendation, the SRC will meet to decide. The SRC will consist of:

1. Trial Statistician
2. OCTO trial management representative
3. Either:
  - a. One Medical Oncologist and one Clinical Oncologist or
  - b. Two Clinical Oncologists

The SRC Charter document for this trial is stored in the TMF and will define the exact membership and who should be present for decisions to be made. Further internal or external experts may be consulted by the SRC, as necessary. Any PI can request an ad hoc SRC meeting at any time in order to facilitate the immediate communication of any emerging safety issues during the course of the trial.

RIOC (Radiotherapy and Imaging Oversight Committee) will act as the TSC and convenes roughly every 6 months. The role of RIOC is to provide oversight for the trial on behalf of the Sponsor and Funder(s) as described in the charter. The RIOC will provide overall supervision of the safe and effective conduct of the trial. The RIOC will review trial progress against agreed milestones, adherence to protocol, and patient safety, and consider new information. The RIOC has responsibility for deciding if the trial needs to be stopped early on grounds of safety or efficacy.

The trial may stop early for safety. In the event that all dose levels are toxic, the trial will stop before reaching the maximum number of patients. If  $P(\text{risk of DLT} > 0.35 | \text{dose} = 1, \text{current data}) > 0.65$  for the lowest dose level and at least three patients have complete data for the toxicity endpoint (a DLT or have completed the toxicity window) we will stop the trial.

### 3.5 Timing of Final Analysis

Primary and secondary outcomes will be analysed after all patients have completed their end of treatment visit, usually at week 13. Analyses for all tertiary outcomes will be documented elsewhere and will not be undertaken by the trial statistician.

### 3.6 Blinded analysis

This is not a blinded trial.

### 3.7 Statistical Analysis Outline

For all analyses, patients will be included according to the treatment schedule to which they are assigned. All patients who receive at least one dose of enadenotucirev, regardless of how much treatment received and follow-up completed, will contribute to analysis. It is therefore important that every effort is made to encourage patients, including those patients who do not receive/complete their allocated treatment, to attend for follow-up clinic visits to avoid bias in the analysis of the results.

All patients enrolled in the trial and who received at least one dose of enadenotucirev will be accounted for and included in the analyses. The number of patients who were not evaluable, who died or withdrew before treatment began will be recorded.

Baseline characteristics will be summarised for all enrolled patients. Patients who died or withdrew before treatment started or do not complete the required safety observations will be described and evaluated separately.

Evaluable for toxicity: All patients will be evaluable for toxicity from the time of their first treatment.

The trial will use the model based design to propose treatment schedules and will be updated prior to each TMG meeting to recommend a treatment schedule for each patient recruited.

## 4. STATISTICAL PRINCIPLES

### 4.1 Statistical Significance and Multiple Testing

There will be no statistical significance level defined for CEDAR as it is a dose-finding trial and schedule recommendations will be based on the posterior probabilities calculated by the dose-toxicity and dose-response models using all available data at each time.

### 4.2 Definition of Analysis Populations

*Main:* all patients who received at least one dose of enadenotucirev.

*Surgical:* All patients who underwent surgery after treatment

*Sensitivity:* Patients who received the full prescribed dose of enadenotucirev, i.e. did not miss any dose, or had a DLT. If a patient is still on treatment and has received their full prescribed dose of enadenotucirev so far, they will be included in this population.

For dose-escalation decisions during the trial, the population analysed will be the main and sensitivity populations. However, for the efficacy endpoint, patients who have not reached this time point yet will not provide any information to the efficacy model. Patients who have reached the time point for this endpoint and did not have the evaluation, withdrew or died prior to evaluation will be treated as non-responders.

## 5. TRIAL POPULATION AND DESCRIPTIVE ANALYSES

### 5.1 Representativeness of Study Sample and Patient Throughput

The flow of participants through each stage of the trial, including numbers of participants assigned to a schedule, receiving intended treatment, completing the study protocol, and analysed for the primary outcome is provided following CONSORT. Protocol violations/deviations and information relating to the screening data including the number of ineligible patients entering the study, together with reasons will be reported. Information on number of participants screened, found to be ineligible (with reasons where available), refused to participate (with reasons where available) will also be included.

A CONSORT diagram will be prepared, an example CONSORT diagram is given in Appendix 3.

### 5.2 Withdrawal from treatment and/or follow-up

Withdrawals/loss to follow-up together with reasons will be reported by treatment schedule.

### 5.3 Baseline Characteristics

Baseline characteristics, including important prognostic, demographic and clinical variables will be reported overall for the main population.

Numbers (with percentages) for binary and categorical variables and means (and standard deviations), or medians (with lower and upper quartiles) for continuous variables will be presented.

## 5.4 Unblinding

The trial is not blinded.

## 5.5 Description of Compliance with Intervention

A summary of enadenotucirev received will be presented by assigned treatment schedule. Compliance to chemotherapy and radiotherapy is a secondary outcome and will be presented as described in Section 6.2.

## 5.6 Reliability

The NAR score will be hand checked for 5 patients.

# 6. ANALYSIS

## 6.1 Outcome Definitions

Primary outcome:

- *Safety*: Binary toxicity measure defined by the occurrence of a DLT or not. This is recorded during the 13 weeks of follow-up after starting treatment. The definition of a DLT is given Appendix 4.
- *Efficacy*: MRI tumour regression grade. This is a 5 point scale that is coded as a binary variable, with scores of 1 or 2 defining a responder and scores of 3, 4 or 5 a non-responder. It is measured at 13 weeks. Patients who did not have the evaluation, or who withdrew or died prior to evaluation will be treated as non-responders. During the trial, for dose-escalation decisions a patient who has not yet reached this time point will not be included in analysis at this decision point. See Appendix 5 for the definition of MRI tumour regression grade

See Section 6.2.1 Primary analysis for definition of the optimal dose.

For dose-escalation interim analyses the safety and efficacy data is taken from the patient status update CRF. For the final determination of the MTD at the end of the trial, the safety outcome will be taken from the *BW135\_DLT\_Assessment* and *BW166\_Adverse\_Events* CRFs and the efficacy outcome taken from the *BW156\_Week13\_Pelvic\_MRI* CRF.

Secondary outcomes:

- Treatment tolerance. This is the amount of capecitabine and radiotherapy received, coded as completing at least 80% of the intended capecitabine dose and at least 20 fractions of radiotherapy. Measured at week 9. Compliance is taken from the *BW150\_Capecitabine* and *BW145\_Radiotherapy* CRF.
- MRI tumour regression grade. See definition for primary outcome, but here it will not be dichotomised. MRI tumour regression grade is taken from the *BW156\_Week13\_Pelvic\_MRI* CRF.
- Pathological complete response. This variable relates to the resected tumour so will only be observed for patients undergoing surgery. It is measured on a 4 point scale, with a score of 1 denoting pathological complete response, and scores 2:4 denoting no pathological complete response. Pathological complete response is taken from the *BW156\_Week13\_Pelvic\_MRI* CRF.
- Neoadjuvant Rectal (NAR) score. This score ranges from 0-100 with a higher score equating to a worse prognosis. It is a derived outcome which components measured on the resected tumour and at initial tumour staging. Therefore, this will only be observed for patients undergoing surgery. It is defined as

- $NAR = \frac{[5pN - 3(cT - pT) + 12]^2}{9.61}$ , where
- cT is clinical tumour stage and is an element of the set {1, 2, 3, 4}
- pT is pathological tumour stage and takes a value in {0, 1, 2, 3, 4}
- pN is pathological nodal stage is in {0, 1, 2}
- pT and pN are taken from the *BW160\_Surgery\_Details* CRF and denoted ypT and ypN, cT is taken from the *BW070\_Screen\_Pelvic\_MRI* CRF.

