#### 5.3.1 Evaluation schedule A

**Pre- Dose – the following assessments can be completed within 72 hours prior to the dose. Vital signs to be completed on day of dosing**

- Adverse events and DLTs since the previous assessment
- New or changes to existing medications
- Physical examination of major body systems
- Weight
- ECOG performance status
- Local laboratory assessments:
  - Urine dipstick – if 2+ or greater proteinuria enadenotucirev dosing should be interrupted pending completion of 24 hour urine collection to exclude significant proteinuria, see further guidance in section 9.3.

- Routine blood samples
  - Haematology – Hb, white blood cells (WBC) with differential count (neutrophils and lymphocytes) and platelets
  - Biochemistry – sodium, potassium, calcium, phosphate, urea, creatinine, total protein, albumin, bilirubin, alkaline phosphatase (alk phos), AST and/or ALT and LDH
  - Coagulation screen (aPTT and INR)

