#### **Renal:**

- Development of proteinuria, 2+ as measured by urinalysis and confirmed with an albumin/creatinine ratio of  $>3\text{g}/\text{mmol}$  with a 24-hour urinary protein  $\geq 1\text{g}/24\text{h}$  or if there is a decline in eGFR (where a decline in eGFR is defined as eGFR  $<60\text{ml}/\text{min}/1.73\text{m}^2$  or a drop in eGFR by 20% from screening, baseline or previous visit), following administration of enadenotucirev, shall be classified as a DLT. No further doses of enadenotucirev will be administered to that patient.

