**Renal injury:** Three patients out of 123 patients (2.4%) have developed significant renal impairment while receiving enadenotucirev. Whilst no confirmed pathophysiology has been identified it is felt to be due to vascular leakage due to cytokine release. Proteinuria of 2+ on a urine dipstick should therefore be further investigated, due to the potential risk of serious renal injury, with 24 hour urine collection for protein/creatinine ratio. If preferable locally, a urine protein- to-creatinine ratio or urine albumin – to – creatinine ratio are also acceptable in lieu of a 24 hour collection test. Additional blood tests should also be up to date including a serum albumin and serum creatinine. A consultation with nephrology is advised for specialist input. Specifically, early specialist intervention for investigation and treatment if decline in renal function is detected will include:

1. Full renal work-up, including examination of urine sediment, discussion with renal team and then commence high dose corticosteroids and then, if further decline in renal function;
2. Renal biopsy, followed by plasmapheresis should be considered with close involvement of the renal team.

No enadenotucirev is to be administered after the development of proteinuria as this constitutes a DLT.

Refer to section 8.5 for guidance on dose modification/ interruption due to toxicity.

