### 13. APPENDIX 4 DEFINITION OF DLT

Definition of DLT as given in Protocol V3.0, 11th August 2019

All patients who have received at least one dose of enadenotucirev will be evaluable for DLTs.

DLTs are defined as any of the following occurring between the start of trial treatment until the Week 13 visit and by the principal investigator (PI) assessed as possibly, probably or definitely related to enadenotucirev or the interaction between enadenotucirev and radiotherapy and/or capecitabine. Patients who experience a DLT will receive no further trial treatment.

Dose limiting toxicities must be reported within 24 hours of the site becoming aware using the SAE form and scan and email as a PDF attachment to [[contact]](mailto:[contact]) and send an email notification to [[contact]](mailto:[contact]).

DLTs will be defined as per NCI CTCAE v4.03, except for proteinuria, and include:

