**Renal:**

- Development of proteinuria, 2+ as measured by urinalysis and confirmed with an albumin/creatinine ratio of  $>3\text{g}/\text{mmol}$ , following administration of enadenotucirev, shall be classified as a DLT. No further doses of enadenotucirev will be administered to that patient.

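### SAP 6.1 defines the primary DLT outcome by Appendix 4, whose renal and fever criteria differ from Protocol 9.1; Protocol 9.3 and 14.4 do not match 9.1 either

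*SAP*

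**What the plan says.** SAP 6.1 makes the safety outcome a yes/no DLT over 13 weeks and states: "The definition of a DLT is given Appendix 4". Appendix 4 begins "Definition of DLT as given in Protocol V3.0" and dates that version to August 2019. SAP 1.2 lists the same source as "Protocol_V3.0_11Aug2020", and Appendix 5 also gives 2020. SAP 1.2 dates V2.0 to November 2019, so the 2019 date for V3.0 must be a slip.

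The renal bullet in Appendix 4 reads "Development of proteinuria, 2+ as measured by urinalysis and confirmed with an albumin/creatinine ratio of" more than 3 g/mmol and sets no further test. Protocol 9.1 opens in the same way, adds a 24-hour urinary protein of at least 1 g, and continues "or if there is a decline in eGFR (where a decline in eGFR is defined as eGFR" below 60 mL/min/1.73 m² or a 20% drop.

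Protocol 9.3 says: "No enadenotucirev is to be administered after the development of proteinuria as this constitutes a DLT". It also says that urine ratios "are also acceptable in lieu of a 24 hour collection test". Protocol 5.3.1 reads as if confirmation is needed first: at 2+ or more, "enadenotucirev dosing should be interrupted pending completion of 24 hour urine collection to exclude significant proteinuria".

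Protocol 14.4 is a reporting table with its own DLT column. Protocol 9.1 and Appendix 4 both say that their lists are not exhaustive and send suspected DLTs to the Chief Investigator and the TMG.

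**The concern.** The DLT is the binary outcome in every toxicity fit, in the early stopping rule and in the final schedule recommendation. A DLT also ends trial treatment for that patient. The SAP fixes this outcome by a list that is not the list sites are given in Protocol 9.1. An analyst who checks events against the SAP would apply different renal and fever rules from the investigator who classified them. A site that reads Protocol 9.3 or 14.4 could also classify an event differently from a site that reads 9.1. No sentence in either document says which text governs.

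The unit matters in its own right. Renal injury is a toxicity that the protocol singles out, and the printed ratio limit weakens the rule meant to catch it.

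**Working it through.** **1. Appendix 4 against Protocol 9.1**

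| Item | SAP Appendix 4 | Protocol 9.1 | Effect |
|---|---|---|---|
| Renal | 2+ and raised ratio | 2+ and raised ratio, with 24-hour protein ≥1 g, or an eGFR decline | Substantive |
| Febrile neutropenia | >38.5 °C | >38.3 °C once, or ≥38 °C for over 1 hour | Substantive |
| Two missed doses | due to toxicity | due to enadenotucirev toxicity | Small: the opening paragraph of Appendix 4 already requires relatedness to enadenotucirev or its interaction with radiotherapy or capecitabine |
| Grade 4 neutropenia | >6 days | ≥7 days | None in whole days |

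The differences run in both directions. A related case with 2+, a raised ratio, 24-hour protein below 1 g and stable eGFR meets the renal bullet only in Appendix 4. A single 38.4 °C with neutrophils below 1.0 × 10⁹/L meets the fever bullet only in 9.1. If an eGFR decline counts alone, which the punctuation of 9.1 leaves open, some renal events are DLTs only under 9.1.

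**2. The unit**

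Both renal bullets print >3 g/mmol; inclusion criterion 8 uses 3 mg/mmol. Assume creatinine excretion of 5–15 mmol/day (not in the documents).

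- 3 g/mmol × 5–15 mmol/day = 15–45 g albumin per day.
- 3 mg/mmol × 5–15 mmol/day = 15–45 mg albumin per day.

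The same bullet in 9.1 uses 1 g/24 h of total protein. A limit equivalent to 15–45 g would almost never be reached, so mg/mmol is very probably meant. The two lists share this error.

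**3. Protocol 9.3 and 14.4 against 9.1**

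- Proteinuria: 9.3 calls its development a DLT and lets a ratio replace the 24-hour collection; 9.1 uses the 24-hour value as a criterion.
- Grade 3 anaemia: 9.1 requires transfusion dependency. 14.4 has no anaemia row, and its row for unlisted grade ≥3 events carries a DLT tick without that condition.
- Withdrawal: 9.1 requires toxicity definitely attributable to enadenotucirev. 14.4 ticks adverse events leading to withdrawal under a heading that includes possible and probable relation.
- Early diarrhoea: 14.4 adds a duration of more than 3 days that 9.1 lacks.
- Late toxicity: radiotherapy ends in week 7, and 7 + 12 = week 19. This is outside the 13-week window, so the tick cannot affect the endpoint.

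**4. What one event can do**

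The documents give no figure to reproduce here. Inputs from SAP 6.2.1: logit p = log(α) + β·log(x/6), x = 1, 2, 4, 6; log(α) ~ N(log(0.3/0.7), 1.44); log(β) ~ N(−0.1, 0.25); target interval (0.2, 0.35); a schedule is safe if P(DLT rate > 0.35) < 0.35. The model was fitted by grid integration with complete follow-up (all weights 1). Assumed data: 0/2 on schedule 1, 0/3 on schedule 2, k/6 on schedule 3.

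| k | P(DLT rate > 0.35), schedule 3 | Same, schedule 4 | Toxicity recommendation |
|---|---|---|---|
| 0 | 0.009 | 0.050 | 4 |
| 1 | 0.049 | 0.177 | 4 |
| 2 | 0.167 | 0.396 | 3 |
| 3 | 0.374 | 0.642 | 2 |
| 4 | 0.617 | 0.834 | 2 |
| 5 | 0.816 | 0.940 | 2 |
| 6 | 0.932 | 0.984 | 1 |

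Three of the six one-event steps change the recommendation (1 to 2, 2 to 3, 5 to 6). From k = 2 to k = 3, schedule 3 crosses the 0.35 safety limit and the recommendation falls from 3 to 2. A full-size example behaves alike: with 3/6/12/9 patients on schedules 1–4 and DLTs 0/1/3/2, schedule 4 is recommended (P about 0.22). One more DLT on schedule 4 raises P to about 0.37 and moves the recommendation to schedule 3.

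**The case against.** Most of the mismatch is openly labelled version lag. Section 9.1 carries the definition heading, 12.1 refers readers to it, and 14.4 is titled as a reporting summary, so a reader can infer that 9.1 governs. Sites assess DLTs under the protocol, suspected cases go to the Chief Investigator and TMG, and the SRC can review them. SAP 6.1 takes the outcome from CRFs and does not say that the statistician re-adjudicates. All of this stands and limits the harm. It does not make the SAP's own definition correct, and case discussion supplies no single rule.

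The renal gap is also narrower than it looks. If enadenotucirev is stopped under 9.3 with two or more doses still due, the patient misses two consecutive doses for enadenotucirev toxicity, which is itself a DLT under 9.1. The gap survives mainly when at most one dose remains or dosing resumes.

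The heading over the disputed 14.4 rows can be read as a condition: how to report events already judged dose limiting. The ticked DLT column allows the other reading, and the text does not choose. That 9.1 is not exhaustive permits additions; it does not settle conflicting conditions on the same event.

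A reader might go further and use the 20% proteinuria listed in 9.2 at 3 × 10¹² vp to estimate how often decisions would change. The documents do not support that. The figure is ungraded, not 2+ confirmed by ratio. An estimate would also need the ratio read as mg/mmol and would have to ignore the missed-dose route. The table shows only that the renal point bears mainly on schedules 3 and 4, since proteinuria is listed at 0% at 1 × 10¹² vp.

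**Conclusion.** The point holds and should be fixed. The SAP defines its primary toxicity outcome by a list whose renal and febrile neutropenia criteria differ from Protocol 9.1. A decision threshold carries a probable unit error in both documents, and 9.3 and 14.4 state DLT conditions that 9.1 does not share.

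The size is bounded. One reclassified event can change the toxicity recommendation but does not always, and the allocated schedule is the minimum of the toxicity and efficacy recommendations, so the efficacy model may hide a change. The frequency and net direction of reclassification are unknown. A reader might infer that patients have been, or will be, misclassified; nothing in the documents shows this, and routine data probably follow 9.1.

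The conclusion rests on taking the supplied protocol as current, since its version page is not available. The model results rest on invented patient counts, complete follow-up and the standard reading of the SAP's logistic model.

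**What to change.** - Replace the Appendix 4 text with a reference to section 9.1 of the current protocol version as the governing DLT list, and correct the 2019 date wherever V3.0 is still cited.
- Rewrite the renal bullet once. Confirm the ratio unit with the clinical team (mg/mmol is expected), state which test confirms proteinuria, and state whether a related eGFR decline counts alone.
- Align 9.3 with that bullet.
- Align the 14.4 DLT ticks with 9.1: restore the conditions for grade 3 anaemia and for withdrawal, settle the early diarrhoea duration, and remove the late-toxicity tick.
- Check DLT decisions already made against the agreed list, and refit the model if any change.

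The cost is protocol and SAP wording plus that check. Changing DLT criteria may count as a substantial amendment under Protocol 23.4, with approvals needed before use. No extra patients are needed.
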